This is the second version of the statistical analysis plan for study protocol, adding the details of the pre-specified preliminary analysis for healthy adolescent/child participants and adults (subgroup CA) 1 month after the second or third doses of BioNTech's BNT162b2 and SinoVac's CoronaVac. Longitudinal immunogenicity analysis describing the decay after vaccination over three years will also be specified for various timepoints. Patients with immune disorders or other pediatric conditions will also be studied and their immunogenicity outcomes compared against healthy counterparts.

2 Introduction

This is the second version of the statistical analysis plan for study protocol, adding the details of the pre-specified preliminary analysis for healthy adolescent/child participants and adults (subgroup CA) 1 month after the second or third doses of BioNTech's BNT162b2 and SinoVac's CoronaVac. Longitudinal immunogenicity analysis describing the decay after vaccination over three years will also be specified for various timepoints. Patients with immune disorders or other pediatric conditions will also be studied and their immunogenicity outcomes compared against healthy counterparts. Interim analyses are performed when all participants in a particular subgroup have completed assessments at each timepoint.

2.1 Study Objectives

Primary objectives

1. Report the frequencies of reactogenicity within the 7 days after each vaccine injection;
2. Compare frequencies of reactions among the vaccines;
3. Report the short-term and long-term (up to 36 months post-vaccination) immunogenicity outcomes including spike protein IgG and related markers, neutralizing antibody titres and B and T cell immune responses;
4. Compare immunogenicity outcomes between children and adults, such that the geometric mean values of immunological parameters are statistically non-inferior (0.6 of adult value) in children, and differences between vaccines in children

Secondary objectives

5. Describe adverse events and serious adverse events during the study period;
6. Explore any parameters or markers predictive and correlative of immune responses to vaccination;
7. Short-term and long-term (up to 36 months post-vaccination) longitudinal differences in non-spike protein antibody titres for participants receiving CoronaVac;
8. Short-term and long-term (up to 36 months post-vaccination) longitudinal differences in type I and II T cell immune responses between vaccines and between children and adults
9. Differences in short-term and long-term (up to 36 months post-vaccination) longitudinal differences in spike protein IgG and related markers, neutralizing antibody titres and cellular immune responses against emerging viral variants between vaccines, and between children and adults;
10. Vaccine breakthroughs as documented by N and ORF8 antibodies in subjects receiving BNT162b2, or ORF8 in subjects receiving CoronaVac, with estimation of potential immunological correlates of protection against infection.
11. Explore the psychosocial impact of COVID-19 vaccination in adolescents
12. Impact of pre-existing conditions on safety, reactogenicity and immunogenicity of vaccines
13. Impact of vaccination on adolescents with previous COVID-19 and long COVID

14. Short-term and long-term (up to 36 months post-vaccination) longitudinal differences in SARS-CoV2 whole blood immune responses between vaccines and between children and adults
15. Short-term and long-term (up to 36 months post-vaccination) longitudinal differences in SARS-CoV2 nasopharyngeal immune responses between vaccines and between children and adults
16. Predict vaccine efficacy based on established immune correlates of protection

2.2 Study Design

2.2.1 Healthy adolescents

This is a single-center, immunobridging study in 200 healthy adolescents aged 11-17 years and their parents or other adult controls, in which participants elect to be immunized against COVID-19 with BioNTech BNT162b2 or SinoVac's CoronaVac. A variety of immunogenicity outcomes will be measured and bridged to their healthy parents to demonstrate respective non-inferiority of the vaccines in adolescents to adults. Reactogenicity and safety will also be described. Participants will be followed-up for a period of 3 years.

2.2.3 Patients living with immunodeficiency or other paediatric diseases

Adolescents living with immunodeficiencies or other paediatric diseases will be recruited in disease subgroups. Safety, reactogenicity and immunogenicity will be described as healthy adolescents. Two or three doses of the vaccines will be given as the trialled primary series. Immunogenicity outcomes will be compared with those of healthy adolescents over 3 years.

3 Endpoints and baseline variables

3.1 Primary endpoints

3.1.1 Reactogenicity endpoints

3.1.1.1 Adverse reactions

For all participants receiving one dose or more under our study protocol, excluding those who already completed immunization prior to joining the study, we solicit prespecified local and systemic reactions for 7 days after immunization with each dose (days 0 to 7). Participants are asked to report these reactions daily and will be reminded if they missed reporting.

Solicited reactions are either local or systemic, and they include:

- Pain at injection site
- Pruritus at injection site
- Swelling, erythema and induration at injection site
- Headache
- Fatigue
- Myalgia
- Nausea
- Diarrhea
- Vomiting
- Arthralgia
- Cough
- Chills
- Fever
- Decreased appetite
- Rhinorrhea
- Nasal congestion
- Sore throat
- Abdominal pain

For listed reactions that are present, participants are to fill in related information as specified for the reaction (fever and swelling, erythema and induration at injection site), or determine the severity according to the following scale:

1. Mild: tolerable, not affecting daily activities
2. Moderate: performance of some daily activities affected
3. Severe: performance of some daily activities prevented

For fever, we determine the severity according to body temperature reported by participant:

1. Mild: 38.0-38.4 degrees Celsius
2. Moderate: 38.5-38.9 degrees Celsius
3. Severe: 39.0 degrees Celsius or higher

For swelling, erythema and induration at injection site, we determine the severity according to the following:

1. Mild: diameter 2.0 to 4.9 cm
2. Moderate: diameter 5.0 to 9.9 cm
3. Severe: diameter 10.0 cm or longer

We analyze the presence and absence of each adverse reaction by maximum severity and use of antipyretic medication on any day from days 0-7 after each dose.

- Presence on any day refers to reported presence on any day between days 0-7.
- Absence on any day refers to no reported presence on any day between days 0-7, either reported absence on all days or reported absence on any day and missing report on other days.
- Missing refers to a continued missing report on all days between days 0-7

3.1.2 Immunogenicity endpoints

3.1.2.1 anti-S IgG levels

We measure SARS-CoV2 full S and S-RBD binding antibody level in sera as a primary immunogenicity endpoint. We report results as OD450 value. Values below the limit of detection will be taken as 0.5 of the lower limit of detection. **Geometric** mean OD450 values will be calculated for each timepoint in each subgroup.

3.1.2.2 Surrogate neutralizing antibody inhibition level

We measure SARS-CoV2 S-RBD antibody ACE2-binding inhibition level in sera as a primary immunogenicity endpoint. We report results as level of inhibition (%). Values below the limit of quantification will be taken as 0.5 of the lower limit of quantification. **Geometric mean** inhibition percentage will be calculated for each timepoint in each subgroup.

3.1.2.3 Neutralizing titers (by plaque reduction neutralization assay)

We measure SARS-CoV2 50% and 90% neutralizing titers by plaque reduction neutralization assay (PRNT50) against a virus isolate obtained early in the pandemic (BetaCoV/Hong Kong/VM20001061/2020) as a primary immunogenicity endpoint. Values below the limit of detection will be taken as 0.5 of the lower limit of detection. Values higher than the upper limit of detection (highest dilution tested) will be imputed as the next theoretical dilution. Geometric mean titers will be calculated for each timepoint in each subgroup.

3.1.2.4 IgG avidity

We measure SARS-CoV2 full S binding antibody avidity in sera as a primary immunogenicity endpoint. We report results as avidity index (%). **Geometric mean** percentages will be calculated for each timepoint in each subgroup.

3.1.2.5 IgG Fc receptor binding antibody

We measure SARS-CoV2 full S FcgRIIIa-binding antibody concentration in sera as a primary immunogenicity endpoint. We report results as OD450 value. Values below the limit of detection will be taken as 0.5 of the lower limit of detection. **Geometric mean** OD450 values will be calculated for each timepoint in each subgroup.

3.1.2.6 Th1 and Tc1 response

We measure the frequency of responsive Th1/Tc1 cells among all peripheral blood mononuclear cells (PBMC) in peripheral heparinized blood as a primary immunogenicity endpoint.

Cell types are defined with the following surface markers and intracellular cytokine staining on flow cytometry against stimulation by all SARS-CoV2 peptide pools for CoronaVac participants or only S peptide pool for BNT162b2 participants:

- Responsive Th1 cells are defined as CD3+ CD4+ IFN-g+ or IL-2+ cells in PBMC
- Responsive Tc1 cells are defined as CD3+ CD8+ IFN-g+ or IL-2+ cells in PBMC

The results will be reported as percentage of parent population: percentage of CD4 T cells or CD8 T cells, as applicable.

Geometric mean percentages will be calculated for each timepoint in each subgroup.

3.2 Secondary endpoints

3.2.1 Adverse events

For all participants receiving one dose or more under our study protocol, excluding those who already completed immunization prior to joining the study, we evaluate unsolicited, volunteered local and systemic adverse events for 28 days after immunization with each dose (days 0 to 28) before receipt of the next dose (at least 21 days for BNT162b2 first dose).

For all participants receiving one dose or more under our study protocol, including those who already completed immunization prior to joining the study, we evaluate unsolicited, volunteered severe adverse events from joining the study, until 36 months after completing immunization. Severe adverse events are defined as adverse events involving any of the following conditions.

1. Hospitalization
2. Life-threatening illness
3. Death
4. Disability or permanent damage, including birth defect of participants' offspring

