Two-dose, healthy evaluable immunogenicity	
All eligible participants who
 
 • Generally healthy without any immunocompromise • received two doses of the vaccine within evaluable window for the vaccine (days 21-28 for arm B, days 28-35 for arm C) • has proven seronegative or unknown at baseline, and • with valid and determinate relevant immunogenicity result for the particular analysis • from a blood sampling taking place within the evaluable window for the post-dose 2 acute time-point (within day 14-42 post-dose 2 and before any further doses) • No important protocol deviations as determined by investigators
Two-dose healthy expanded immunogenicity	
All eligible participants who
 
 • Generally healthy without major immunocompromise • Received two doses of the vaccine, • Has proven seronegative or unknown at baseline, • with valid and determinate relevant immunogenicity result for the particular analysis between 7-56 days post-dose 2
Two-dose, all evaluable immunogenicity	
All eligible participants who
 
 • received two doses of the vaccine within evaluable window for the vaccine (days 21-28 for arm B, days 28-35 for arm C) • with valid and determinate relevant immunogenicity result for the particular analysis • from a blood sampling taking place within the evaluable window for the post-dose 2 acute time-point (within day 14-42 post-dose 2 and before any further doses) • No important protocol deviations as determined by investigators
Two-dose all expanded immunogenicity	
All eligible participants who
 
 • Received two doses of the vaccine, • With valid and determinate relevant immunogenicity result for the particular analysis between 7-56 days post-dose 2
Three-dose, healthy evaluable immunogenicity	
All eligible participants who
 
 • Generally healthy without any immunocompromise • received three doses of the vaccine; dose 3 at least 84 days after dose 1 • has proven seronegative or unknown at baseline, and not known to be infected • with valid and determinate relevant immunogenicity result for the particular analysis • from a blood sampling taking place within the evaluable window for the post-dose 3 acute time-point (within day 13-42 post-dose 3 and before any further doses) • No important protocol deviations as determined by investigators

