6.2 Secondary endpoints

6.2.1 Adverse events

We analyze unsolicited adverse events based on the following:

- Estimand: Percentage of participants reporting an adverse event (by medDRA terms)
- Analysis set: (healthy) safety population

- Time-point: after each dose on days 0-28, before the next dose
- Statistics: incidence (events per person), n and N

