7.2 Interim analysis 2 (Jan 2022)

Interim analysis will be performed in Jan 2022 when 100 healthy participants have completed post-dose 2 assessment under the age of 18 years, including at least 50 for PRNT, for each vaccine.

While paediatric patients with prior COVID-19 and severe paediatric/immune conditions have been enrolled in this trial, the analysis of these participants will be separate. Safety, reactogenicity and immunogenicity analyses will focus on healthy participants.

Key objectives of this analysis are to describe the reactogenicity and safety of these vaccines in the pediatric age group, compare the acute immunogenicity of the vaccines in adolescents and adults, and compare the acute immunogenicity of the two vaccines in adolescents. We aim to demonstrate non-inferiority in a range of immunogenicity endpoints in adolescents to adults.

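### Dose-1 unsolicited adverse events are summarised over windows that can differ in length between the two vaccines, with no common window set

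*SAP*

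**What the plan says.** SAP 3.2.1 sets the window for unsolicited events as "for 28 days after immunization with each dose (days 0 to 28) before receipt of the next dose (at least 21 days for BNT162b2 first"; the bracketed minimum is an exception for dose 1 of that vaccine alone. SAP 6.2.1 repeats the rule as "after each dose on days 0-28, before the next dose". Its estimand is the percentage of participants reporting an event, and its statistic line reads "Statistics: incidence (events per person), n and N". Neither measure has a time denominator, and no window common to both vaccines is defined.

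The second-dose timing comes from SAP 4.2. The two-dose evaluable immunogenicity sets require that a participant "received two doses of the vaccine within evaluable window for the vaccine (days 21-28 for arm B, days 28-35 for arm C"). The safety sets in SAP 4.3 ask only for one dose and some safety data, with no condition on the interval.

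Unsolicited events are a secondary, descriptive endpoint (SAP 2.1, objective 5). A key objective of the second interim analysis in SAP 7.2, which covers both vaccines, is to "describe the reactogenicity and safety of these vaccines in the pediatric age group".

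**The concern.** A count that stops at the next dose depends on when the next dose is given. If the two vaccines have different dose intervals, two groups with the same true event rate and the same onset pattern will show different dose-1 figures. The same applies within BNT162b2: dose 1 can be cut at day 21, while dose 2 normally has its full 28 days, because the three-dose evaluable sets in SAP 4.2 place dose 3 at least 84 days after dose 1.

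At stake is how the safety tables are read. A lower dose-1 incidence for BNT162b2 than for CoronaVac, or a rise from BNT162b2 dose 1 to dose 2, could come partly from the length of the window. With no test planned, readers have only the raw figures to go on.

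**Working it through.** The SAP states no event rate, onset distribution or precision for unsolicited events, so there is no figure to reproduce.

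**Inputs from the SAP**
- Window: to day 28 or the next dose, whichever is first (3.2.1, 6.2.1).
- Dose 2 on days 21-28 for arm B and 28-35 for arm C (4.2). Arm B is read as BNT162b2 and arm C as CoronaVac, in line with the 21-day remark in 3.2.1.
- Target of 120 participants per regimen and age group (5.1.2).

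**Assumptions**
- Same true 28-day event rate and onset pattern for both vaccines.
- CoronaVac recipients have the full 28 days.
- Second dose of BNT162b2 on day d, with d = 21 or 24.5 (the midpoint of 21-28).

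**Share of 28-day events seen by day d**
- Constant onset: d/28. Day 21: 21/28 = 0.75, a 25% shortfall. Day 24.5: 24.5/28 = 0.875, a 12.5% shortfall. Day 28: none. Counting calendar days over days 0-28, the day-21 ratio is 22/29 = 0.76 with the day of dose 2 included, or 21/29 = 0.72 with it excluded.
- Early-clustered onset, exponential with half-time h, truncated at 28 days: (1 - 2^(-d/h)) / (1 - 2^(-28/h)).

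| Half-time h | Shortfall, d = 21 | Shortfall, d = 24.5 |
|---|---|---|
| 7 days | 1 - 0.875/0.9375 = 6.7% | 2.8% |
| 10 days | 10.5% | 4.6% |
| 14 days | 1 - 0.646/0.75 = 13.8% | 6.3% |

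- Alternative pattern, with share f of events in days 0-7 and the rest even over days 7-28. The ratio at day 21 is f + (1 - f) x 14/21. For f = 50%, 70% and 90% this gives 0.83, 0.90 and 0.97.

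**What a table would show**
- Take a true 28-day incidence of 20% for both vaccines with constant hazard. CoronaVac reads 20%. BNT162b2 reads 1 - 0.8^(21/28) = 15.4% at day 21, or 1 - 0.8^(24.5/28) = 17.7% at day 24.5.
- BNT162b2 dose 2 against dose 1 with equal constant rates: 1/0.875 = 1.14 to 1/0.75 = 1.33, an apparent rise of 14 to 33%.

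**Against sampling error**
- With 120 per group, the 95% half-width for a difference between two proportions near 20% is 1.96 x sqrt(2 x 0.2 x 0.8/120) = 10 percentage points. The artefact above is 2.3 to 4.6 points.
- With constant onset and every second dose on day 21, a two-sided 5% test would detect the artefact about 9% of the time at 0.10 events per person, and about 22% at 0.40.

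**Checking two remedies**
- Common window, days 0-20: the expected ratio is 1.00 for any onset pattern, provided nobody has dose 2 before day 21.
- Events per person-day to the earlier of day 28 or dose 2: the ratio is 1.00 only with constant onset. With dose 2 on day 21, a 7-day half-time gives 0.933 x 28/21 = 1.24 and a 14-day half-time gives 0.862 x 28/21 = 1.15. The BNT162b2 rate is then 15 to 24% too high, where the SAP's statistic is 7 to 14% too low.

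**The case against.** A reader might infer that the plan makes BNT162b2 look safer by design. The SAP does not support that, for these reasons:

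- **No planned comparison is affected.** Objective 5 is to describe events, and 6.2.1 names no test or contrast between vaccines or doses. Fisher's exact test in 6.1.1.1 covers solicited reactions over days 0-7, where the windows are equal. SAP 7.2 describes safety and compares immunogenicity.
- **The cut-off is not hidden.** SAP 6.2.1 states that counting stops at the next dose, and 3.2.1 gives the 21-day minimum.
- **The 28 days for CoronaVac are inferred.** They rest on immunogenicity definitions. The safety sets fix no interval, so actual windows may differ in either group, and a BNT162b2 recipient with a late or no second dose keeps the full window.
- **Events are attributed elsewhere, not lost.** An event after an early second dose falls in the dose-2 window, and severe events are followed to 36 months for both vaccines.
- **The groups are not randomised.** Participants elect their vaccine (2.2.1), so crude incidences are not like for like in any case.

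All five stand, and they limit the point to one descriptive table. They do not remove it. The 21-day exception is stated in the adverse-event section itself for BNT162b2 dose 1 alone, and stating it does not adjust for it. On the dosing windows in 4.2, the distortion runs in one direction. Two vaccines reported in the same analysis will probably be read side by side, though that is a judgement about readers and not something the SAP plans.

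**Conclusion.** The point holds as a reporting weakness in a secondary, descriptive table. Dose-1 figures for the two vaccines, and BNT162b2 dose 1 against dose 2, are not on the same basis. The relative shortfall for BNT162b2 dose 1 is 0 to 25%. The upper end needs constant onset and every second dose on day 21. With onset half-times of 7 to 14 days it is about 3 to 14%, and with every second dose on day 28 it is zero. All of these sizes rest on assumed onset patterns and on dose timing taken from the immunogenicity sets. A true difference between the vaccines could outweigh the effect, and at 120 per group it is smaller than sampling error. It biases no hypothesis test and gives no ground for saying that the plan favours one vaccine.

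**What to change.** In SAP 6.2.1:

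1. Add a summary of dose-1 unsolicited events for both vaccines over a common window of days 0-20, and flag participants who received dose 2 earlier.
2. Use the same window after dose 2 wherever doses are set side by side.
3. Keep the 0-28 day figures, and show the follow-up time per group beside them.
4. Do not use a person-day rate as the comparative measure in their place. It is unbiased only under a constant event rate and would overstate BNT162b2 dose 1 if events cluster early.

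The cost is SAP wording and one extra summary. Dose dates and onset dates are already needed to apply the stated window. Late dose-1 events drop out of the common-window table but stay in the 0-28 day figures.

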3.2.2 Vaccine efficacy prediction

We predict vaccine efficacy for recipients of each vaccine based on neutralizing antibody correlate of protection, as published by Khoury et al in Nature Medicine, 2021. Geometric mean neutralizing titers in participants receiving either vaccines will be normalized against that of a set of house convalescent controls as fold of convalescent titers, and protective efficacy against symptomatic disease will be predicted based on the published model.

3.2.3 anti-N and N-CTD IgG levels

We measure SARS-CoV2 full N and N-CTD binding antibody levels in sera as a primary immunogenicity endpoint. We report results as OD450 value. Values below the limit of detection will be taken as 0.5 of the lower limit of detection. Geometric mean OD450 values will be calculated for each timepoint in each subgroup.

3.2.4 Correlates of immunogenicity

Correlations between primary immunogenicity outcomes will be evaluated by Pearson correlation coefficients after natural log transformation, with a more stringent significance level with lower alpha to account for multiple comparison testing. Relationships between immunogenicity outcomes and baseline variables such as age, sex and haematological parameters will be explored by multiple linear regression by vaccine type and age subgroup.

3.3 Participant characteristics

Demographic variables obtained include age at time of dose 1 (in years), sex (male or female), medical history (generally healthy, pre-existing COVID-19 or immunodeficient), pre-existing conditions (coded according to medDRA) and concomitant medications.

4 Analysis sets

4.1 Total enrolled population

Population	Description
Enrolled	All participants with a signed informed consent form, screened in as included by study physician and received at least one dose of study vaccine

4.2 Immunogenicity populations

Population	Description
Single-dose, healthy evaluable immunogenicity	All eligible participants who 
 • Generally healthy without any immunocompromise • received at least one dose of the vaccine, • has proven seronegative or not known to have had previous COVID-19 infection, • with valid and determinate relevant immunogenicity result for the particular analysis • from a blood sampling taking place within the evaluable window for the post-dose 1 acute time-point (no more than 3 days earlier or later than day 21 for arm B or day 28 for arm C, and before dose 2), and • no important protocol deviations as determined by investigators
Single-dose healthy expanded immunogenicity	All eligible participants who 
 • Generally healthy without major immunocompromise • Received one dose of the vaccine, • Has proven seronegative or unknown at baseline, • with valid and determinate relevant immunogenicity result for the particular analysis at least 14 days post-dose 1 but before dose 2
Single-dose, all evaluable immunogenicity	All eligible participants who 
 • received at least one dose of the vaccine, • with valid and determinate relevant immunogenicity result for the particular analysis • from a blood sampling taking place within the evaluable window for the post-dose 1 acute time-point (no more than 3 days earlier or later than day 21 for arm B or day 28 for arm C, and before dose 2), and • no important protocol deviations as determined by investigators
Single-dose all expanded immunogenicity	All eligible participants who 
 • Received one dose of the vaccine, • With valid and determinate relevant immunogenicity result for

	the particular analysis at least 14 days post-dose 1 but before dose 2
Two-dose, healthy evaluable immunogenicity	
All eligible participants who
 
 • Generally healthy without any immunocompromise • received two doses of the vaccine within evaluable window for the vaccine (days 21-28 for arm B, days 28-35 for arm C) • has proven seronegative or unknown at baseline, and • with valid and determinate relevant immunogenicity result for the particular analysis • from a blood sampling taking place within the evaluable window for the post-dose 2 acute time-point (within day 14-42 post-dose 2 and before any further doses) • No important protocol deviations as determined by investigators
Two-dose healthy expanded immunogenicity	
All eligible participants who
 
 • Generally healthy without major immunocompromise • Received two doses of the vaccine, • Has proven seronegative or unknown at baseline, • with valid and determinate relevant immunogenicity result for the particular analysis between 7-56 days post-dose 2
Two-dose, all evaluable immunogenicity	
All eligible participants who
 
 • received two doses of the vaccine within evaluable window for the vaccine (days 21-28 for arm B, days 28-35 for arm C) • with valid and determinate relevant immunogenicity result for the particular analysis • from a blood sampling taking place within the evaluable window for the post-dose 2 acute time-point (within day 14-42 post-dose 2 and before any further doses) • No important protocol deviations as determined by investigators
Two-dose all expanded immunogenicity	
All eligible participants who
 
 • Received two doses of the vaccine, • With valid and determinate relevant immunogenicity result for the particular analysis between 7-56 days post-dose 2
Three-dose, healthy evaluable immunogenicity	
All eligible participants who
 
 • Generally healthy without any immunocompromise • received three doses of the vaccine; dose 3 at least 84 days after dose 1 • has proven seronegative or unknown at baseline, and not known to be infected • with valid and determinate relevant immunogenicity result for the particular analysis • from a blood sampling taking place within the evaluable window for the post-dose 3 acute time-point (within day 13-42 post-dose 3 and before any further doses) • No important protocol deviations as determined by investigators
Three-dose healthy	All eligible participants who

expanded immunogenicity	
 ● Generally healthy without major immunocompromise ● Received three doses of the vaccine; dose 3 at least 56 days after dose 1 ● Has proven seronegative or unknown at baseline, and not known to be infected ● with valid and determinate relevant immunogenicity result for the particular analysis between 6-56 days post-dose 3
Three-dose, all evaluable immunogenicity	
All eligible participants who
 
 ● received three doses of the vaccine; dose 3 at least 84 days after dose 1 ● with valid and determinate relevant immunogenicity result for the particular analysis ● from a blood sampling taking place within the evaluable window for the post-dose 3 acute time-point (within day 13-42 post-dose 3 and before any further doses) ● No important protocol deviations as determined by investigators
Three-dose all expanded immunogenicity	
All eligible participants who
 
 ● Received three doses of the vaccine, ● With valid and determinate relevant immunogenicity result for the particular analysis between 6-56 days post-dose 3

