6.1.2 Immunogenicity endpoints

For immunogenicity endpoints, primary analyses of primary endpoints (including non-inferior hypotheses) are conducted in the evaluable immunogenicity populations. Secondary analysis will also be performed in the expanded population.

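### The two-dose expanded sets do not require sampling before a third dose, so a sample taken after an early dose 3 can count as a two-dose response in the secondary analyses

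*SAP*

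**What the plan says.** Section 4.2 of the SAP defines evaluable and expanded immunogenicity sets after one, two and three doses, each in a healthy and an all-participant version.

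- **Two-dose expanded (healthy and all).** The sampling condition is "with valid and determinate relevant immunogenicity result for the particular analysis between 7-56 days post-dose 2". The healthy version adds health and baseline serostatus conditions. Neither version says anything about later doses, and neither sets a window for dose 2.
- **Two-dose evaluable (healthy and all).** Dose 2 must fall in its window ("days 21-28 for arm B, days 28-35 for arm C") and the sample must be taken "within day 14-42 post-dose 2 and before any further doses".
- **Single-dose expanded (healthy and all).** The result must come "at least 14 days post-dose 1 but before dose 2".
- **Three-dose evaluable.** The dosing condition is "received three doses of the vaccine; dose 3 at least 84 days after dose 1".
- **Three-dose healthy expanded.** The dosing condition is "Received three doses of the vaccine; dose 3 at least 56 days after dose 1", with a result "between 6-56 days post-dose 3".
- **Three-dose all expanded.** The sampling window is the same, but no minimum interval to dose 3 is stated.

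Section 6.1.2 places the primary analyses, including the non-inferiority hypotheses, in the evaluable sets. It then adds: "Secondary analysis will also be performed in the expanded population".

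**The concern.** The expanded sets are meant to relax timing, and the two-dose versions do so: the window grows from days 14-42 to days 7-56 after dose 2. In the same step the condition that ties the sample to the second dose is dropped. The SAP kept the equivalent condition when it relaxed the single-dose window, so the omission does not look like a deliberate feature of expanded sets.

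At stake is the meaning of a two-dose result in these sets. If third-dose responses enter, the two-dose geometric mean rises wherever dose 3 boosts the readout, and the contrast between the second and third dose shrinks. A geometric mean ratio (adolescent to adult, vaccine to vaccine, route to route, or diseased to healthy) shifts if early third doses are more common on one side. The all-participant set has the least protection, because its three-dose counterpart has no minimum interval and section 2.2.3 foresees either two or three doses as the primary series in patients.

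**Working it through.** The SAP states no figure to reproduce here. The check is day arithmetic on the section 4.2 windows.

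**Inputs**

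- Dose 2 on schedule: day 21-28 (arm B) or 28-35 (arm C) after dose 1. This is the evaluable-set window; the expanded sets have none.
- Earliest dose 3: day 56 after dose 1 (three-dose healthy expanded) or day 84 (three-dose evaluable).
- Two-dose expanded sampling window: days 7-56 after dose 2.
- Three-dose expanded sampling window: days 6-56 after dose 3.
- Planned post-dose-3 time point in section 6: two weeks after dose 3.

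**Formulas**

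- Gap from dose 2 to dose 3: g = (day of dose 3) − (day of dose 2).
- Samples taken after dose 3 but inside the two-dose window: days g+1 to 56 after dose 2, which exist only if g ≤ 55.
- Samples that also meet the three-dose expanded window: days g+6 to 56, which exist only if g ≤ 50.
- A sample two weeks after dose 3 falls on day g+14, inside the two-dose window only if g ≤ 42.

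**Results (days counted after dose 2)**

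| Arm | Dose 2 day | Dose 3 day | g | After dose 3, in two-dose window | In both expanded windows | Two weeks after dose 3 |
|---|---|---|---|---|---|---|
| B | 21 | 56 | 35 | 36-56 | 41-56 | 49 (inside) |
| B | 28 | 56 | 28 | 29-56 | 34-56 | 42 (inside) |
| C | 28 | 56 | 28 | 29-56 | 34-56 | 42 (inside) |
| C | 35 | 56 | 21 | 22-56 | 27-56 | 35 (inside) |
| B | 21 | 84 | 63 | none | none | 77 (outside) |
| B | 28 | 84 | 56 | none | none | 70 (outside) |
| C | 28 | 84 | 56 | none | none | 70 (outside) |
| C | 35 | 84 | 49 | 50-56 | 55-56 | 63 (outside) |

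With dose 3 on day 56, the planned post-dose-3 sample lands on days 42-49 (arm B) or 35-42 (arm C) after dose 2, always inside the two-dose expanded window.

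With dose 3 on day 84, overlap needs g ≤ 55, so dose 2 on day 84 − 55 = 29 or later. That never happens in arm B on schedule, and in arm C it happens only in the later part of the schedule. A late dose 2 widens the overlap: once dose 2 falls on day 84 − 42 = 42 or later, the planned post-dose-3 sample is again inside the window.

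**Where the sets are used.** The expanded sets are listed for the geometric means and ratios in sections 6.1.2.1 to 6.1.2.12, 6.2.3, 6.2.4, 6.2.6 and 6.2.7. Predicted efficacy (6.2.2) and the correlations (6.2.5) use the evaluable sets only.

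**After the fix.** If the sample must precede any further dose, the overlap is zero days in every row.

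**The case against.** **Two doses might mean exactly two.** That reading does not hold. The two-dose evaluable sets use the same wording on doses and still add the limit on further doses. The single-dose expanded sets likewise require one dose and still require sampling before the next. An exact count would also exclude everyone who later had a third dose, although the evaluable set keeps them, so the expanded set would no longer contain the evaluable one.

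**The time-point labels separate the samples.** Section 6 lists one month after dose 2 and two weeks after dose 3 separately, and sections 6.4.2.2 and 6.4.3.1 count samples and doses outside their windows. This makes confusion less likely in practice. It does not exclude a post-dose-3 sample under the written rule, because set membership is decided by the day 7-56 window.

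**Day 56 is an eligibility floor, not a schedule.** This stands. The overlap needs an early dose 3 or a late dose 2, and the SAP gives no frequency for either. At the 84-day floor, with dose 2 on schedule, almost nothing overlaps.

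**The primary conclusion is safe.** This also stands. A reader might infer that contamination threatens the non-inferiority result, and might set an assumed inflation beside the 1.67-fold margin. The documents do not support that. Sections 5.1.1 and 6.1.2 run those tests in evaluable sets, which carry the limit. If a share p of the samples follows dose 3 and dose 3 multiplies the readout by r, the geometric mean is multiplied by r^p, but the SAP gives neither p nor r. Equal contamination in both groups, with the same r, cancels in a ratio.

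**Conclusion.** The defect is real and confined to secondary analyses. As written, both two-dose expanded definitions can classify a sample taken after dose 3 as a two-dose response, and from the sixth day after dose 3 the same sample can also count as a three-dose response. This is a stated eligibility rule that misclassifies, not merely missing detail.

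Its reach depends on dose timing. With dose 3 on day 56 and dose 2 on schedule, the planned post-dose-3 sample falls on days 35-49 after dose 2 and qualifies. With dose 3 on day 84 or later and dose 2 on schedule, overlap is nil in arm B and at most the seven days 50-56 in arm C, of which only days 55-56 allow double counting. A later dose 2 widens both.

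It would go too far to say that every immunogenicity result is affected, or that the bias has a known size. The affected outputs are the expanded-set geometric means and geometric mean ratios. The number of affected samples, and any resulting shift, cannot be derived from the SAP. The arithmetic rests only on the section 4.2 windows and on dose 2 being given on schedule where so stated.

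**What to change.** In section 4.2, add to the two-dose healthy expanded and the two-dose all expanded definitions the condition already in the two-dose evaluable sets: the sample must be taken before any later dose. This concerns which samples enter an analysis set and does not touch dosing.

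The cost is one clause in each definition. The dose and sampling dates needed to apply it are already required by the existing windows. A few samples may leave the two-dose expanded sets; those taken 6 to 56 days after dose 3 remain available to the three-dose expanded sets if the other criteria are met.
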